Implementation of onsite, rapid ART initiation among People Who Inject Drugs living with HIV at Syringe Services Program

Protocol Version 2

Protocol Version Date 4/25/22

eProst ID Number 20200793

PI [name]

NCT Number NCT04650269

- 1) **Protocol Title:** Implementation of onsite, rapid ART initiation among People Who Inject Drugs (PWID) living with HIV at Syringe Services Program (SSP)

- 2) **Objectives***

Aim 1: To evaluate/assess the effectiveness and feasibility of same-day rapid initiation of ART for PWID living with HIV who utilize the SSP (*SSP Rapid Initiation*).

Aim 2: To identify barriers to success of HIV care retention and treatment adherence among PWID preparing for entry into long-term HIV care.

Aim 3: To compare adherence of patients in *SSP Rapid Initiation* after transition to a traditional healthcare clinic.

- 3) **Background***

PWID experience extensive barriers to engagement in HIV care. Challenges in linkage to care, retention in care, and viral suppression in PWID are well documented, with estimates that less than half of PWID living with HIV in the U.S. are virally suppressed^{5,6}. In the 2018 Miami outbreak investigation and public health response in PWID, we were able to support 100% of newly infected individuals in achieving viral suppression through a test-and-treat approach with intensive patient navigation and medication management; but faced challenges in initiating ART in previously diagnosed PWID, with only 53% achieving suppression. Reasons for this sub-optimal result could include recognized barriers to HIV care and retention within the Miami community, including drug use, mental illness, stigma and transportation issues^{7,8}. Although Miller et al.⁹ recently reported that intensive and flexible patient navigation with psychosocial counseling was central to increased initiation of ART and viral suppression, the literature on evidence-based approaches to initiation of ART and retention in care for PWID is lacking.

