We plan to utilize a hybrid quasi-experimental design to test the effectiveness and implementation outcomes of successful delivery of rapid ART initiation intervention in an SSP (Figure 1). In addition, we will use a multi-method approach, collecting both quantitative and qualitative data on patients (n=50) accepting the rapid ART initiation protocol at the SSP, patients declining to engage in the rapid ART initiation protocol, and patients after transition to a traditional Ryan White clinic. To assess the effectiveness of the *SSP Rapid Initiation*, we will compare the percentage of PWID virally suppressed at 6 months post baseline at the SSP compared to at 6 months post transition to UM/Jackson Adult Outpatient HIV Clinic. Since this proposed study is in its pilot phase, this study will not be examining differential effects in treatment groups in the study, but rather provide preliminary data to support a future randomized-controlled trial. Represented in the figure below, participants at the SSP will be tested for HIV using a rapid test, which when reactive will be confirmed using a second rapid HIV test from another manufacturer following a CDC-approved dual rapid HIV testing algorithm. If a patient tests positive, the patient will be offered immediate initiation onto ART at the SSP. Baseline labs (4th Generation HIV test, HIV viral load, CD4, HIV genotype, CBC, CMP, Gonorrhea/Chlamydia, RPR, HCV Antibody, HCV RNA, HbsAg, HBsAb, HAV Total) will be obtained and sent to the Miami-Dade County Health Department. Patients will have up to 7 days post HIV-positive test to start on ART (per definition of rapid ART initiation). The community advisory board and peer navigators at the SSP will assist in the *SSP Rapid Initiation* protocol design, execution, and process improvement. Peers will work between the SSP and the Ryan White clinics. Our experience with the 2018 HIV cluster in PWID in Miami taught us that medication management (i.e., pill lockers at the SSP, third party pickup of ART at ADAP by SSP staff, weekly medication drops to participants unable to access medications at the fixed site) was highly effective at supporting adherence in PWID living with HIV. Peer navigators will conduct outreach to *SSP Rapid Initiation* participants, monitor appointments, and provide transport to healthcare services. This intensive linkage and active follow-up delivered by peer PWID living with HIV is essential to delivery of care to this population. Peers will be tasked with helping participants with eligibility (e.g., Ryan White, Medicaid) and ADAP enrollment when they transition to the transitional HIV clinic. This grant will enable them to have ongoing support in clinic after transition to the traditional healthcare environment for long-term care.

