For this proposed study, we expect that ongoing, peer-driven patient navigation based at the SSP will result in patients' remaining virally suppressed after transition to the UM/Jackson Adult Outpatient HIV Clinic. More importantly, based on the hybrid design, this study will lay the foundational groundwork to provide a proof of concept for HIV care at SSPs, including pertinent implementation information for future expansion sites in the state of Florida. We expect to uncover barriers and facilitators to implementation of rapid ART initiation at an SSP, including patient-level perspectives on improving delivery of care developed in the *SSP Rapid Initiation among PWID Living with HIV* protocol.

Secondary outcomes: Time to viral suppression, or viral suppression at 1 month, will be assessed. Treatment adherence will be assessed both by follow-up viral load results (1, 3, 6, 9, 12 months) as well as by medication management measures (e.g., PWID accessing meds weekly, pill counting by SSP staff) and attendance at clinic visits. Successful transition to HIV care at a Ryan White clinic will also be assessed. The clinic-based peer patient navigator will assist in transition of patients to long-term care within six months of ART initiation. Ryan White clinic appointment attendance and successful re-enrollment in Ryan White/ADAP will be assessed.

9) Data and Specimen Banking*

For clinical data, we will use the UHealth's electronic health record, UChart, which is locked under dual authentication.

All data collected will be housed in the REDCap database system, which is locked under dual authentication by University of Miami Information Technology and then extracted for analysis by the principal investigator. Only study staff will have access to survey results.

As for the in-depth interviews, sessions will be audio-recorded, transcribed by an external company, de-identified for analysis and stored on a password-protected computer in a secured office in the Don Soffer Clinical Research Center. Only study staff will have access to results.

10) Data Management*

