Quantitative Data Analysis: Quantitative data will be analyzed using descriptive statistics and frequencies to present pilot data on rapid ART initiation at an SSP. Data will be presented as frequency tables, and viral suppression will be reported as a percentage suppressed at each time-point (1, 3, 6, 9, 12 months). All quantitative data will be stored and managed in REDCap and all analyses will be performed using SAS statistical software (Version 9.4; SAS Institute, Cary, NC). Categorical data will be analyzed using frequency of responses and continuous variables will be analyzed using means and standard deviations.

Qualitative Data Analysis: Qualitative data collected from the in-depth interviews will be analyzed using general inductive methodology³¹, which allows for themes to be developed from the raw data based on a study objective/research question. A data codebook will be generated in an iterative process during transcript reading by the study team. All qualitative data analysis will be conducted using Dedoose (version 8.2.14, Sociocultural Research Consultants, Los Angeles, CA), a cross-platform software used for analyzing qualitative and mixed methods research.

11) Risks to Subjects*

Study procedures: there is risk of discomfort to phlebotomy, but no risk above routine HIV care

Study Drug: Serious risks of taking BFTAF includes serious drug reactions such as lactic acidosis, hepatomegaly with steatosis, hepatotoxicity, hepatitis B virus exacerbation, pancreatitis, nephrotoxicity, neutropenia, immune reconstitution syndrome, autoimmune disorders, suicidality, and angioedema. Common adverse reactions include diarrhea, headache, fatigue, hyperbilirubinemia, elevated CK, abnormal dreams, dizziness, insomnia, hypercholesterolemia, hyperamylasemia, neutropenia, LFTs elevated, nausea/vomiting, depression, rash, dyspepsia, abdominal pain, asthenia, increased creatinine, bone density loss, arthralgia/myalgia, cough, paresthesia, peripheral neuropathy, palmar-plantar hyperpigmentation, hypertriglyceridemia, hematuria, hyperglycemia, glycosuria, rhinitis and flatulence.

12) Adverse Events and Serious Adverse Events

AEs will be any of the common adverse reactions defined above. SAEs will include any hospitalization or death or disability that occurs with participants in the trial. AEs will be reported to the IRB in continuing reviews. SAEs will be reported to the IRB within 24 hours.

13) Potential Benefits to Subjects*

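### The plan expects patients to keep viral suppression after moving to the clinic, but its specified summaries do not show how many of the same people did

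*Combined protocol and SAP*

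**What the plan says.** Section 8 (Primary Endpoints) states the expectation that peer navigation "will result in patients' remaining virally suppressed after transition to the UM/Jackson Adult Outpatient HIV Clinic". Aim 3 in Section 2 concerns the same patients "after transition to a traditional healthcare clinic", and the Section 8 table gives viral suppression as its patient-level outcome.

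Two places say how viral load will be summarised:

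- Section 10 (Data Management, Quantitative Data Analysis) says that "viral suppression will be reported as a percentage suppressed at each time-point (1, 3, 6, 9, 12 months". Its general method is that "Quantitative data will be analyzed using descriptive statistics and frequencies to present pilot data on rapid ART initiation at an SSP", and "Categorical data will be analyzed using frequency of responses".
- Section 5 (Study Design) adds: "we will compare the percentage of PWID virally suppressed at 6 months post baseline at the SSP compared to at 6 months post transition". It does not say whether the same people enter both percentages, or what the denominator is.

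Section 8 also names time to suppression (or suppression at 1 month) and adherence judged from follow-up viral loads, with no method for either. No section defines maintained or lost suppression, plans a before/after table, or says how a missing viral load counts.

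**The concern.** Staying suppressed is a property of a person: below 200 copies/ml before the move and still below it afterwards. A percentage per visit, or two such percentages set side by side, describes the group at each time. Someone who first becomes suppressed after the move offsets someone who loses suppression, and the percentage does not change. Such late suppressors are plausible here, because Section 8 has the peer navigator help patients move within six months of starting ART, so some may move before they are suppressed. Time to suppression does not fill the gap, since it measures reaching suppression and not keeping it.

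At stake is how Aim 3 is read. Similar percentages before and after transition would invite the conclusion that patients kept their suppression, although the same figures could also fit a sizeable loss after leaving the SSP. The pilot is meant to inform a randomized trial and expansion sites, so the difference matters.

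**Working it through.** The plan states no power, effect size or expected suppression rate for this cohort, so there is no figure to reproduce. The check asks how much two percentages reveal about the number who stayed suppressed.

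**Inputs.** n = 50 (Section 18), single arm (Section 6), suppression below 200 copies/ml (Section 8). The Background reports 53% suppressed among previously diagnosed people and 100% among newly infected people in the 2018 outbreak response. Neither is a forecast for this cohort or a rate after transition. Rates from 50% to 90% are therefore assumed, with all 50 measured at both times.

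**Formula.** Let *a* be the number suppressed before and *b* the number suppressed after, among the same *n*. The number suppressed at both times lies between max(0, *a* + *b* − *n*) and min(*a*, *b*). Dividing by *a* gives the range for the percentage maintained.

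**Worked case, 70% and 70%.** *a* = *b* = 35. Lower limit: 35 + 35 − 50 = 20, so 20/35 = 57.1%, with 15 losses offset by 15 gains. Upper limit: 35/35 = 100%, with no losses.

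**Range of assumed rates** (exact Clopper-Pearson 95% intervals in brackets):

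| Before / after | Suppressed at both | Lowest maintained | Highest maintained |
|---|---|---|---|
| 50% / 50% | 0 to 25 of 25 | 0% (0 to 14%) | 100% (86 to 100%) |
| 60% / 60% | 10 to 30 of 30 | 33% (17 to 53%) | 100% (88 to 100%) |
| 70% / 70% | 20 to 35 of 35 | 57% (39 to 74%) | 100% (90 to 100%) |
| 80% / 80% | 30 to 40 of 40 | 75% (59 to 87%) | 100% (91 to 100%) |
| 90% / 90% | 40 to 45 of 45 | 89% (76 to 96%) | 100% (92 to 100%) |
| 80% / 70% | 25 to 35 of 40 | 62.5% (46 to 77%) | 87.5% (73 to 96%) |

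At 100% and 100% the bound closes: 50 + 50 − 50 = 50 of 50. Only results near that extreme settle the question. If different people are missing at the two times, the percentages no longer share a denominator and even these limits need not hold.

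**Which viral load counts as after transition.** If transition is at month *m*, six months later is month *m* + 6. With viral loads at months 6, 9 and 12, the nearest is month 9 or 12 whenever *m* + 6 exceeds 7.5, that is, *m* above 1.5. The documents give no distribution of transition dates. Because transition may come before month 6, the 6-month value used in Section 5 may itself be taken after the move.

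**Whether those viral loads exist.** The Section 5 text, the Section 7 schedule table, and Sections 8 and 10 include months 9 and 12. The Section 7 text lists months 1, 3 and 6 only and speaks of patients leaving the trial at transition.

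**The case against.** The strongest reply is that this is a small descriptive pilot. Its patient-level outcome for Aim 3 contains no maintenance criterion, and staying suppressed is only a stated expectation. That is true, and it limits the weight of the point. It does not answer it, because a before/after table and one percentage are also descriptive and need no test or power calculation. Section 5's disclaimer about differential effects concerns treatment groups, not change within a person.

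A second reply is that the plan leaves room for the right analysis. A reader might infer that no percentage could show maintained suppression, whatever its denominator. The documents do not support that: Section 5 states no denominator, and if the later percentage were taken among those suppressed before transition, it would be the maintained percentage. What stands is that neither this denominator nor a cross-tabulation is specified. Comparing two overall percentages leaves the ranges above as they are, even in identical patients.

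A third reply is that the low ends are extreme. They are: at 70% and 70%, 57% requires all 15 unsuppressed people to become suppressed while 15 others lose suppression. They show what the summaries leave open, not what is likely.

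A reader might also infer that pairing would sharpen the estimated change. That depends on how many people change status. With 4 losses and 4 gains the paired half-width is 1.96 × √8 / 50 = 11 points, but with 15 and 15 it is 1.96 × √30 / 50 = 21 points, against 1.96 × √(2 × 0.7 × 0.3 / 50) = 18 points if the two 70% figures are treated as independent. Section 10 plans no interval in any case, so precision is not the argument.

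**Conclusion.** The point holds as an inexpensive improvement to the analysis. The expectation concerns individuals, while the specified summaries are a percentage per visit and a comparison of two aggregate percentages with pairing and denominator unstated. Under the assumed rates, with all 50 measured twice, equal percentages leave maintained suppression anywhere from 0% to 100% (at 50%), 57% to 100% (at 70%), 75% to 100% (at 80%) or 89% to 100% (at 90%). The size depends on rates that the documents do not give, and the gap closes as suppression approaches 100%.

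A reader might go further and infer that Aim 3's conclusion would be wrong. The documents do not support that. They show that the conclusion would be undetermined on this point if the plan were followed as written. Aim 1 is not affected.

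**What to change.** Add to Section 10:

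> Aim 3: among participants who transition and whose last HIV RNA on or before transition is <200 copies/ml, report the number and percentage with HIV RNA <200 copies/ml at the scheduled viral load closest to 6 months after transition (month 9 or 12 for most), with an exact 95% CI. Participants with no post-transition value stay in the denominator as not shown to be maintained. Show the before/after table (suppressed, not suppressed, missing) with the numbers lost and gained. Report participants who never transition separately.

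Keep the per-visit percentages as description.

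The Section 7 text on viral load timing must be reconciled with the Section 5 text, the Section 7 schedule table, and Sections 8 and 10. The change needs no new data only if the month 9 and 12 viral loads are taken and the transition date is recorded.

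The cost is one paragraph and a smaller denominator: 25 to 45 people instead of 50 across the assumed rates, fewer if some never transition. The interval is correspondingly wider; for example, 30/40 gives 75% (59% to 87%).

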Lab Assessments	HIV Rapid	HIV Ag/Ab Test HIV RNA CD4 count HIV genotype CBC CMP GC/CT RPR HCV Ab HCV RNA HBsAg anti-HBs Anti-HAV Total	HIV RNA CD4 count CBC CMP GC/CT RPR	HIV RNA CD4 CBC CMP GC/CT RPR	HIV RNA CD4 CBC CMP GC/CT RPR	HIV RNA CD4 CBC CMP GC/CT RPR	HIV RNA CD4 CBC CMP GC/CT RPR
Assessments	Eligibility	Baseline		Quant/Qual	Quant/Qual		Quant/Qual

Participants at the SSP will be tested for HIV using a rapid test, which when reactive will be confirmed using a second rapid HIV test from another manufacturer following a CDC-approved dual rapid HIV testing algorithm. Confirmatory testing no longer requires venipuncture. A 4th generation test will be sent as indicated below. The initiation of care, however, will not be delayed. If a patient tests positive on dual rapids, the patient will be offered immediate initiation onto ART at the SSP. If accepted, they will provide informed consent. They will have an immediate HIV care visit with a provider in person or via encrypted Zoom technology. A prescription for BFTAF will be written and filed for the participant, and BFTAF will be provided on site. ART will be initiated immediately, and in the rare case that changes in dosing or ART based on lab values (e.g. creatinine) is needed,

they will made once lab results return. This is now standard of care nationwide for rapid initiation. The care visit will be documented in UChart. Baseline labs (4th Generation HIV test, HIV viral load, CD4, HIV genotype, CBC, CMP, Gonorrhea/Chlamydia, RPR, HCV Antibody, HCV RNA) will be obtained and sent to the Miami-Dade County Health Department. Patients will have up to 7 days post HIV-positive test to start on ART (per definition of rapid ART initiation).

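### Section 12 defines adverse events by the common reactions only, so a listed serious risk without hospitalization, death or disability has no stated route to the IRB

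*Combined protocol and SAP*

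**What the plan says.** Section 11 (Risks to Subjects) describes the drug's risks in two sentences. The first gives serious reactions, ending with "pancreatitis, nephrotoxicity, neutropenia, immune reconstitution syndrome, autoimmune disorders, suicidality, and angioedema". The second gives common reactions, among them "hyperamylasemia, neutropenia, LFTs elevated, nausea/vomiting, depression, rash, dyspepsia, abdominal pain, asthenia, increased creatinine".

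Section 12 (Adverse Events and Serious Adverse Events) defines two classes: "AEs will be any of the common adverse reactions defined above. SAEs will include any hospitalization or death or disability". Reporting follows the classes: "AEs will be reported to the IRB in continuing reviews. SAEs will be reported to the IRB within 24 hours".

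Section 12 does not mention the serious reactions of Section 11. The available text has no life-threatening or medically important criterion, and no catch-all for other untoward events.

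Safety information is collected elsewhere in the plan:
- Section 9: "For clinical data, we will use the UHealth's electronic health record, UChart".
- Section 7, visit table: blood count and metabolic panel at months 0, 1, 3, 6, 9 and 12. The month 1 entry, for example, reads "HIV RNA CD4 count CBC CMP GC/CT RPR".
- Section 5, quantitative assessments of those accepting rapid ART: a side effect inventory and mental health screening at follow-up.

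**The concern.** A definition of AE normally starts wide, and seriousness is then a subset of it. Here the AE class is tied to the milder of two adjacent lists, and the SAE class is described by three outcomes. A reaction that the protocol itself calls serious can fall between the two if it is managed without admission and leaves no disability.

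Care is delivered at a syringe services site or a mobile unit, so serious reactions managed outside hospital are a realistic case. Followed as written, the safety record sent to the IRB could include rhinitis and flatulence yet omit angioedema or suicidality. The study is also meant to supply preliminary data for a randomized trial and to guide expansion sites, so a record filtered by list membership would carry forward.

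**Working it through.** The protocol states no figure on this point, so the check compares Sections 11 and 12.

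**Inputs, counted from Section 11.**
- Serious risks, 11: lactic acidosis, hepatomegaly with steatosis, hepatotoxicity, hepatitis B virus exacerbation, pancreatitis, nephrotoxicity, neutropenia, immune reconstitution syndrome, autoimmune disorders, suicidality, angioedema.
- Common reactions: 31 terms, from diarrhea to flatulence.
- Named on both lists: 1 (neutropenia).

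**Section 12 applied literally.**

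| Event | Named as a common reaction? | Class | Stated IRB route |
|---|---|---|---|
| Any event with hospitalization, death or disability | Irrelevant | SAE | 24 hours |
| Rhinitis, none of those outcomes | Yes | AE | Continuing review |
| Neutropenia, none of those outcomes | Yes | AE | Continuing review |
| Hepatotoxicity, nephrotoxicity or pancreatitis, none of those outcomes | Not by name; raised liver tests, creatinine and amylase are listed | AE for the laboratory finding only | Continuing review for the laboratory finding; none stated for the diagnosis |
| Angioedema, suicidality, immune reconstitution syndrome or lactic acidosis, none of those outcomes | Not by name | Neither | None stated |
| Event on neither list, none of those outcomes | No | Neither | None stated |

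**How far the gap extends.** By identical term, 11 − 1 = 10 serious risks are not named as common reactions. Looser matching shrinks this. The loosest rule tried accepts nine matches:
- neutropenia by name (1);
- the three laboratory counterparts in the table (3);
- hepatitis B exacerbation and hepatomegaly with steatosis through raised liver tests (2);
- suicidality through depression, and angioedema through rash (2);
- lactic acidosis through general symptoms such as nausea or abdominal pain (1).

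That is 1 + 3 + 2 + 2 + 1 = 9, which leaves 11 − 9 = 2: immune reconstitution syndrome and autoimmune disorders. The protocol states none of these pairings. They show only that the count depends on the rule, and that no rule tried brings it to zero. A matched event would also reach the IRB as a laboratory value or symptom, not as the serious diagnosis.

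**The case against.** The strongest reply is that none of the wording is closed. The serious risks are introduced by *such as*, the common reactions by *include*, and SAEs by *will include*. An investigator could properly report angioedema under that language. This stands, and it limits the point: no route is stated, but reporting is not forbidden. It does not remove the point, because open wording leaves classification to individual discretion.

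Three other replies also stand in part. Every hospitalization, death or disability is reported within 24 hours whatever its cause, so the gap concerns only events without those outcomes. Listed laboratory terms give some serious events a partial route. The text between the Section 13 heading and Section 17 was not available, so a further safety provision there cannot be excluded; Section 12 itself appears complete.

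A reader might infer more than the documents support:
- **That 10 of the 11 serious risks go unreported.** The count of 10 requires identical terms, treats open lists as exhaustive, and ignores both the SAE outcomes and the related common terms.
- **That such events go unrecorded.** Clinical records, scheduled laboratory tests, the side effect inventory and mental health screening all provide capture. The content of the inventory is not given, so it cannot be equated with the common list.
- **That neutropenia has an ambiguous route because it is on both lists.** Section 12 separates it by outcome: SAE if it leads to hospitalization, death or disability, otherwise AE. That is one route per event.

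**Conclusion.** The AE definition is wrong as written and should be changed. It points to the common reactions, passes over the serious risks listed immediately before them, and has no catch-all. As a result, a named serious risk that is not also a listed common reaction, or an event on neither list, has no stated route to the IRB when it has none of the three outcomes.

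The size cannot be given as a single number. The count of uncovered risks depends on the matching rule, and the documents give no rates for these events, so no expected number is claimed. No endpoint, sample size or power figure is affected.

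The conclusion rests on a literal reading of Section 12 and on the text that was available. Confidence is medium, because of the open wording and the missing text.

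**What to change.** Reconcile Sections 11 and 12.

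- **Preferred:** define an AE as any untoward medical occurrence during study participation, listed or not, and give both Section 11 lists as examples.
- **Minimum:** add the Section 11 serious risks to the AE definition. The named terms go from 31 to 31 + 11 − 1 = 41, and all 11 serious risks then reach the IRB at least at continuing review. Events on neither list that lack an SAE outcome would still be left out.
- **With either:** have the investigator state whether any events beyond hospitalization, death or disability also go by the 24-hour route. Which events those should be is for the investigator to decide.

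The cost is one or two sentences in Section 12, with no new tests or visits. The downside is somewhat more events to log and report in about 50 participants, more under the preferred wording than under the minimum.
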